1.4.2 Secondary Endpoints

Secondary outcomes at 30 days are as follows:

- 1. All-cause mortality
- 2. New Myocardial Injury post-randomisation (New MINS)
- 3. Individual MACE components (including type of arrhythmia)
- 4. Complications (including AKI, infection, delirium)
- 5. Proportion of participants transfused; volume of blood transfused per patient
- 6. Discharge destination (home, other hospital, nursing home, other)
- 7. Acute hospital length of stay
- 8. ED-5D-5L

Additional secondary outcomes at 120 days are as follows:

- 1. All cause mortality
- 2. Secondary care costs
- 3. Unplanned hospital readmissions
- 4. Mobility (as defined by NHFD or SHFA dataset
- 5. Residential status (as defined by NHFD or SHFA dataset)
- 6. EQ-5D-5L
- 7. Health services resource use

Clinical outcomes will be measured until acute hospital discharge or 30 days post randomisation whichever is soonest. Death, readmission, mobility, residential status, quality of life and resource use will be measured at 120 days post-randomisation.

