To address the possibility that any component of the primary outcome (particularly Atrial fibrillation (AF) or new MINS) is much more prevalent in the trial than expected and dominates the primary composite outcome, we propose the following: all the individual components of MACE and new MINS will be reported as secondary outcomes and an a priori sensitivity analysis is undertaken with the AF and new MINS components of the primary outcome removed. This will be pre-specified in the statistical analysis plan when developed and proposed as a secondary analysis.

Secondary outcomes will be analysed using logistic regression for binary outcomes and linear regression for normally distributed continuous outcomes. Continuous outcomes that are not normally distributed will be analysed using appropriate non-parametric techniques. Time to event data will be analysed using an appropriate survival model (e.g., Cox proportional hazards).

Pre-specified sub-group analyses will explore effects in relation to gender, age (<80 vs. \geq 80 years), presence of pre-existing CVD and use of anticoagulant and antiplatelet drugs. These will be analysed as per the primary outcome but including a covariate*treatment interaction.

No interim analysis is planned.

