9.3 ECONOMIC EVALUATION

Full details of the economic evaluation will be specified in a comprehensive Health Economic Analysis Plan (HEAP) (35) authored by the study health economist(s), and signed off by the Chief Investigator prior to analysis.

Two forms of analyses will be undertaken: A cost-consequence analysis (CCA) of the 120-day observed trial period, and longer-term economic modelling.

NHS and PSS (personal social services) will be collected, including details of the initial surgical admission (including complications and recovery period), readmissions, A&E, a, outpatient admissions, any ongoing care packages related to recovery, calls to NHS24/NHS Direct, and primary care. These will be combined with standard UK price weights (36, 37) to generate costs with base year selected as the latest year for which at least 1 participant provides data, and price weights are available. Most of the resource use will be extracted retrospectively from medical records at 120 days, though some top-up self-report may be necessary for minor aspects, particularly around primary care.

The CCA will present these as a profile of NHS and PSS utilisation and cost as additional contextual information alongside health outcomes (including the EQ-5D-5L) without attempting to combine data and estimate Incremental cost per Quality Adjusted Life Years (QALY). This

CR007-T02 v0.5 Page **43** of **69**

IRAS 299977/308830

Version 5.0 26Jun2024

will comprise of univariate mean EQ-5D-5L scores, rates of resource use, and associated costs (type and total) presented for each trial arm alongside differences in means (intervention minus control) and associated 95% confidence intervals. Missing data will be imputed using appropriate techniques depending on degree of missingness, likely multiple imputation by chained equations (which is considered gold standard in this area). (38)Though we note that most important cost factors such as inpatient readmission and care packages will be obtained from medical records and are therefore anticipating high levels of completeness.

The formal assessment of long run cost-effectiveness will be undertaken using decision analytic modelling to account for potential health and cost implications of transition to care home, other rehabilitation programs or care in the community.

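### Section 9.2's normality condition puts EQ-5D-5L and costs under two unreconciled rules and can remove the covariate-adjusted mean difference

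*Protocol*

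**What the plan says.** Section 9.2 gives three rules for secondary outcomes:

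- Binary outcomes go to logistic regression, and linear regression is kept for those continuous outcomes that are normal.
- For the other continuous outcomes the rule reads: "Continuous outcomes that are not normally distributed will be analysed using appropriate non-parametric techniques". No technique or effect measure is named, and no outcome is exempted.
- Time-to-event outcomes go to a survival model, with Cox as the example, without saying which outcomes this covers.

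The continuous secondary outcomes in section 1.4.2 include "Secondary care costs" and EQ-5D-5L at 120 days (EQ-5D-5L also at 30 days), "Acute hospital length of stay" and "volume of blood transfused per patient". Section 1.3.2 opens with quality of life at 120 days and costs as the secondary objective.

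Section 9.3 describes a cost-consequence analysis of the 120-day trial period. EQ-5D-5L means (described as univariate), rates of resource use, and costs are to be "presented for each trial arm alongside differences in means (intervention minus control) and associated 95% confidence intervals". No normality condition is attached. Section 9.2 falls under a statistical analysis plan and section 9.3 under a separate Health Economic Analysis Plan (HEAP). Neither section refers to the other for the outcomes they share.

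**The concern.** The rule in section 9.2 lets the shape of the data decide what is estimated. A normal outcome gets a mean difference; a non-normal one gets whatever the chosen technique targets, which need not be a mean. The outcomes concerned are poor candidates for normality. Costs are plausibly right-skewed and EQ-5D-5L is bounded. Under section 5.2.1 the liberal arm receives a unit soon after randomisation while the restrictive arm receives none until haemoglobin reaches its lower threshold, so zero volumes should gather in the restrictive arm. The protocol states none of this about shape, but it is the reasonable expectation.

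Two things are at stake. First, 120-day EQ-5D-5L and costs could be reported twice, once under each plan, on different scales and with different messages, with no stated rule for which one answers the objective. Second, section 9.3 fixes only univariate EQ-5D-5L means. Linear regression in section 9.2 is the natural route to a mean difference adjusted for baseline, and the normality condition can close it. Baseline EQ-5D-5L is already collected (section 5.2.2 and the schedule in section 6), so the gain in precision costs no further data.

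**Working it through.** There is no protocol figure to reproduce. The check compares the sections outcome by outcome, then asks whether the normality condition is needed.

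**1. Which rule reaches which outcome**

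| Outcome (1.4.2) | Under 9.2 if not normal | Under 9.3 | Result |
|---|---|---|---|
| Secondary care costs | non-parametric, effect measure unnamed | difference in means, 95% CI | two rules, no cross-reference |
| EQ-5D-5L at 120 days | same | difference in means, 95% CI; arm means univariate | two rules; no baseline-adjusted mean difference fixed |
| Blood volume | same | not named | no mean difference fixed anywhere |
| Acute length of stay | same, or a survival model | not named; the initial admission enters resource use and cost | method open |

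**2. Is normality needed to compare means?**

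Inputs: 507 per arm (section 9.1). The distributions are assumptions, because the protocol gives none: log-normal costs with log-SD s = 0.6 in one arm and 1.0 in the other, 4,000 simulated trials per scenario. A Wilcoxon-Mann-Whitney test is compared with a large-sample difference in means allowing unequal variances.

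For a log-normal, mean = median × exp(s²/2).

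*Scenario A: equal means of 15,000.*
- Medians: 15,000 × exp(−0.18) ≈ 12,529 and 15,000 × exp(−0.50) ≈ 9,098.
- Probability that a cost from the less spread arm exceeds one from the other: Φ((0.50 − 0.18)/√(0.36 + 1.00)) = Φ(0.274) ≈ 0.608.
- Null standard error of that probability at 507 per arm: √((2 × 507 + 1)/(12 × 507²)) ≈ 0.0181, so z ≈ 0.108/0.0181 ≈ 6.
- Simulated: the rank test rejects in 100% of trials and the mean-difference test in 5.2%. The 95% CI for the mean difference covers zero in 94.9%.

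*Scenario B: equal medians of 10,000.*
- True mean difference: 10,000 × (exp(0.18) − exp(0.50)) ≈ 11,972 − 16,487 ≈ −4,515.
- Simulated: the rank test rejects in 5.4% and the mean-difference test in 99.9%. CI coverage is 94.6%.

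The Monte Carlo standard error of a coverage near 95% with 4,000 trials is √(0.95 × 0.05/4,000) ≈ 0.34 percentage points, so both coverages agree with 95%.

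**3. Reading the result**

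Rank tests and mean comparisons answer different questions when the arms differ in shape. At this size a mean comparison keeps its coverage under marked skew, so a normality check protects nothing. Fewer than 507 per arm may have a 120-day EQ-5D-5L because of deaths and non-response. The documents give no figure for that number, but the argument needs only several hundred per arm.

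**The case against.** A reader might infer more than the text supports. Five replies stand, in whole or in part.

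- *Mean differences for costs and EQ-5D-5L are lost.* They are not. Section 9.3 plans them with 95% CIs.
- *Sections 9.2 and 9.3 contradict each other.* That is too strong. A clinical analysis under the SAP and an economic analysis under the HEAP can both be done. The defect is an overlap that nobody has reconciled, and it cannot extend to blood volume or length of stay, which section 9.3 does not name.
- *The rule means an unadjusted rank test.* Section 9.2 speaks of techniques, not of a test. It names Koch's non-parametric ANCOVA, with adjustment, for the primary outcome, and a bootstrap of the mean is also non-parametric. The adjusted mean difference can therefore be lost, but need not be.
- *The method will be picked after seeing results by arm.* Nothing says so. Section 9.2 promises a SAP agreed before database lock.
- *Length of stay should also be a mean difference.* The protocol leaves a survival model open. With an assumed 30-day mortality of 7%, an early death counts as a short stay, so a mean is itself debatable.

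It can also be said that naming a technique for each outcome is SAP work. That is fair for the detail. It does not answer the point that the protocol itself states a condition, normality, which is unnecessary and which a SAP would either inherit or have to depart from.

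**Conclusion.** The point holds as a modest correction. Section 9.2 ties the analysis of continuous secondary outcomes to a normality condition that is not needed at about 507 per arm. On its face the condition reaches both outcomes of the first secondary objective, for which section 9.3 already asks for mean differences. The two sections should give one estimate, and at present nothing makes them do so. For blood volume no mean difference is fixed in either section.

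No sample size, power or error rate in the protocol changes. The simulation illustrates a principle under assumed distributions. It does not show that a rank analysis would miss or reverse a cost difference in this trial, and the documents contain nothing from which that could be estimated. The conclusion rests on two assumptions: that at least some of these outcomes will not be normal, and that section 9.2 applies to costs and EQ-5D-5L because section 1.4.2 lists them as secondary outcomes and no exception is made.

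**What to change.** In section 9.2, replace the normality-dependent rule for these outcomes with the following:

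- EQ-5D-5L and costs are analysed as differences in means with 95% CIs, by linear regression with robust or bootstrap standard errors whatever the distribution. The model adjusts for the stratification factors (centre, age group, pre-existing cardiovascular disease) and, for EQ-5D-5L, its baseline value.
- Sections 9.2 and 9.3 report this same estimate, and the SAP and HEAP refer to each other on it.
- Volume of blood transfused is reported as a mean difference with a robust or bootstrap CI, beside the proportion transfused. The two already stand together in section 1.4.2 ("Proportion of participants transfused; volume of blood transfused per patient").
- Rank-based tests are supportive only.
- The method for length of stay is left to the SAP, because early deaths shorten stay.

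The cost is a few sentences in the protocol, carried into the SAP and HEAP, and no new data. The downside is slightly wider intervals for heavy-tailed outcomes. How deaths enter the EQ-5D-5L mean is a separate question that this change does not settle.

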9.3 ECONOMIC EVALUATION

Full details of the economic evaluation will be specified in a comprehensive Health Economic Analysis Plan (HEAP) (35) authored by the study health economist(s), and signed off by the Chief Investigator prior to analysis.

Two forms of analyses will be undertaken: A cost-consequence analysis (CCA) of the 120-day observed trial period, and longer-term economic modelling.

NHS and PSS (personal social services) will be collected, including details of the initial surgical admission (including complications and recovery period), readmissions, A&E, a, outpatient admissions, any ongoing care packages related to recovery, calls to NHS24/NHS Direct, and primary care. These will be combined with standard UK price weights (36, 37) to generate costs with base year selected as the latest year for which at least 1 participant provides data, and price weights are available. Most of the resource use will be extracted retrospectively from medical records at 120 days, though some top-up self-report may be necessary for minor aspects, particularly around primary care.

The CCA will present these as a profile of NHS and PSS utilisation and cost as additional contextual information alongside health outcomes (including the EQ-5D-5L) without attempting to combine data and estimate Incremental cost per Quality Adjusted Life Years (QALY). This

CR007-T02 v0.5 Page **43** of **69**

IRAS 299977/308830

Version 5.0 26Jun2024

will comprise of univariate mean EQ-5D-5L scores, rates of resource use, and associated costs (type and total) presented for each trial arm alongside differences in means (intervention minus control) and associated 95% confidence intervals. Missing data will be imputed using appropriate techniques depending on degree of missingness, likely multiple imputation by chained equations (which is considered gold standard in this area). (38)Though we note that most important cost factors such as inpatient readmission and care packages will be obtained from medical records and are therefore anticipating high levels of completeness.

The formal assessment of long run cost-effectiveness will be undertaken using decision analytic modelling to account for potential health and cost implications of transition to care home, other rehabilitation programs or care in the community.

The model structure will be developed with input from clinical experts. Its parameters will be populated using trial data (including costs and EQ-5D-5L where appropriate), targeted (non-systematic) literature searches, or as a last resort, through formal expert opinion elicitation. To maximise UK policy relevance, the model will follow NICE reference case recommendations (43) including: Adoption of an NHS and personal social service(PSS) costing perspective; cost-utility approach (results presented in terms of incremental cost per QALY calculated from EQ-5D-5L data); discount rate of 3.5% for both costs and QALYs; and the use of probabilistic sensitivity analysis (PSA), most likely generated via a method of moments approach. (44) Choice of primary analysis cost per QALY threshold and EQ-5D-5L scoring algorithm will be selected to match NICE preferences at time of data lock to allow for potential changes in recommendations between trial start and analysis.

10 ADVERSE EVENTS

Adverse Event (AE) and Serious Adverse Event (SAE) reporting will follow the ACCORD SOP for non-CTIMP trials (CR006).

Transfusion Related Adverse Events or Reactions and Serious Transfusion Related Adverse Reactions will be recorded in accordance with the definitions of SHOT (Serious Hazards of Transfusion), revised December 2019. Imputation of any transfusion related AE, AR or SAE will also be assessed according to the definitions given within the SHOT guidance (see Appendix B)

https://www.shotuk.org/wp-content/uploads/myimages/SHOT-Definitions-update-10.01.20- FINAL.pdf

10.1 DEFINITIONS

10.1.1 Adverse Event (AE)

Any untoward medical occurrence in a study participant, which does not necessarily have a causal relationship with the study intervention.

IRAS 299977/308830

Version 5.0 26Jun2024

10.1.2 Adverse Reaction (AR)

Any untoward and unintended response that has occurred due to the intervention.

10.1.3 Transfusion Related Adverse Reaction (AR) or Event

Any untoward and unintended response to a transfused blood component.

10.1.4 Serious Adverse Event (SAE) or Serious Adverse Reaction (SAR) OR Serious Transfusion Related Adverse Reaction

A serious adverse event (SAE) is defined as an untoward occurrence that:

- results in death.
- is life-threatening.
- requires hospitalisation or prolongation of existing hospitalisation.
- results in persistent or significant disability or incapacity.

An SAE occurring to a research participant should be investigated at a local level by the local PI and then reported to the CI and sponsor when, in the opinion of the local PI, the event was either

- Related it resulted from administration of any of the research procedures And / or
 - Unexpected the type of event is not listed in the protocol as an expected occurrence.

10.2 IDENTIFYING AND REPORTING AEs AND SAEs

10.2.1 Assessment of Transfusion Reactions

As mentioned above, transfusion related reactions will be assessed in accordance with the definitions and imputability as set out by SHOT but will also be recorded as an AE on the trial database. All Serious Transfusion Related Adverse Reactions will be recorded as part of the trial data collection process.

Examples include:

- Incorrect or incompatible blood transfusion
- Serious adverse reactions to blood transfusion including (but not exclusively):
- Allergic/febrile transfusion reactions occurring at any time up to 24 hours following a transfusion of a blood component
- Acute or delayed Haemolytic transfusion reaction
- Post transfusion Purpura (thrombocytopenia)
- Transfusion associated graft vs host disease
- Transfusion associated circulatory overload
- Transfusion associated dyspnoea
- Transfusion associated acute lung injury
- Transfusion transmitted infection

IRAS 299977/308830

Version 5.0 26Jun2024

10.2.2 AEs and SAEs that do not require reporting

This study enrols older, anaemic participants who have undergone major emergency surgery and it is expected that many of these participants will suffer medical complications, with consequences up to and including death. Only complications considered by the local PI, or delegated authority, to be *related to the use of study procedures* and not a typical and frequently reported complication of admission to hospital with hip fracture should be reported as AEs. Complications that fall into this category but are defined as endpoint events in protocol section 1.4, e.g. cardiac events, will be recorded as outcome events (whether they are deemed to be related to the use of study procedures or not). Common hospital complications of hip fracture are listed in the table below:

Common complications of admission to hospital with hip fracture
Electrolyte disturbance, including, but not limited to hypo or hypernatremia, hypo or
hyperkalaemia.
Anaemia*
AKI
Delirium*, acute confusional state
Cognitive impairment, chronic or acute
Venous thromboembolic Disease
Respiratory: Chest infection pneumonia, sepsis
Cardiac*: myocardial infarction, acute coronary syndrome, atrial fibrillation, another arrhythmia, *
Cerebrovascular: Stroke or transient ischaemic attack
Infection*
Urinary infection
Pressure sores
Skin ulcers
Immobility
Fall
Death
Complications of surgical fixation of fractured hip
Wound complications
Impaired wound healing
Haematoma
Mechanical malfunction [dislocations, cutting-out, refracture]
Infections
non/malunion

* Complications that are recorded as part of the outcome measures are detailed in the protocol.

10.2.3 Duration of AE and SAE reporting

AE and SAE reporting will start from the time of randomisation in the trial. AEs and SAEs will only be reported during the intervention period, namely from randomisation until the time of acute hospital discharge or 30 days whichever is soonest. Important events that might constitute

CR007-T02 v0.5 Page **46** of **69**

IRAS 299977/308830

Version 5.0 26Jun2024

AEs and SAEs that may plausibly be associated with the intervention are being recorded as part of trial follow up data collection at 120 days post-randomisation.

10.2.4 Reporting and follow up of AEs and SAEs

AE and SAE data will be recorded by the Investigator(s) (or a member of the research team with delegated responsibility to do so) on the Case Report Forms (CRF) and/or SAE report form. Investigators will record all AEs in the AE log in a timely fashion (usually at the time of detection). AEs and SAEs will be followed up until outcome of recovered, recovered with sequelae or death of the study participant.

10.3 ASSESSMENT OF AEs

Each AE must be assessed for seriousness, causality, severity, and expectedness by the Principal Investigator (PI) or another suitably qualified physician in the research team who is trained in recording and reporting AEs and who has been delegated this role. During PI absences appropriately qualified, experienced, and trained site staff may assess causality and report SAEs if they have been delegated this responsibility on the delegation log by the PI.

10.3.1 Assessment of seriousness

The Investigator will assess seriousness (as defined in section 11.1).

10.3.2 Assessment of Causality

The Investigator will assess whether the AE is likely to be related to the study intervention according to the following definitions:

Unrelated: where an event is not considered to have occurred because of the study intervention.

Possibly Related: The nature of the event, the underlying medical condition, concomitant medication, or temporal relationship make it possible that the AE has a causal relationship to the study intervention.

Where there are two assessments of causality (e.g., between PI and Chief Investigator (CI)), the causality assessment by the Investigator cannot be downgraded. If there is a difference of opinion, both assessments will be recorded, and the "worst case" used for reporting purposes.

10.3.3 Assessment of Expectedness

If the AE is judged to be related to the study intervention, the Investigator will assess expectedness.

- Expected The type of event is expected within the study population or intervention
- *Unexpected* The type of event was not listed in the protocol or documents/literature as an expected occurrence

IRAS 299977/308830

Version 5.0 26Jun2024

